6.1.4.9 Visit 12 – Week 96 (or End of Study Visit)

The following procedures will be conducted at Week 96 (Visit 12, ± 30 days, or end of study visit) following IMP administration:

- ETDRS visual acuity testing performed prior to pupil dilation.
- Humphrey Visual Field 30-2 testing performed prior to pupil dilation.
- SD-OCT performed after pupil dilation.
- Pelli-Robson contrast sensitivity testing performed prior to pupil dilation.
- Farnsworth-Munsell 100 Hue color vision test performed prior to pupil dilation.
- Color fundus photos if necessary for grading ocular inflammation.
- Recording of AEs and SAEs.
- Recording of any changes and additions to concomitant medications and any changes in concomitant medication dose or regimen, including supplements.

6.2 Premature Discontinuation

Subjects who discontinue participation in the study prematurely (i.e. prior to Visit 12) will complete an end-of-study visit including all procedures listed for Visit 12.

A subject will be withdrawn from the study under any of the following circumstances:

- Subject's request at any time for any reason.
- Physician's determination that subject's further participation in the protocol is not in the subject's best interest.
- The Sponsor's decision.
- Health Authorities' decision.

For any discontinuation, the Investigator will obtain all the required details and document the date of and the reason for the discontinuation in the case report form (CRF). If possible, Week 48 ETDRS visual acuity should be obtained.

If the reason for withdrawing from the study is an AE, the specific event will be recorded in the CRF.

6.3 Unscheduled Visits

Unscheduled visits may be performed anytime during the study to assess or follow up adverse events, at the subject's request, or at the request of the investigator. The date and reason for the unscheduled visit should be recorded in the source documentation.

If unscheduled visits occur, the Investigator must record the following in the subject's source document and CRF:

- Any AEs.
- Reason for unscheduled visit.
- Recording of any changes or additions to concomitant medications dose or regimen.
- Any clinical assessments, vision and non-vision related, deemed appropriate for the clinical care of the subject.

Unscheduled visits should not alter the timing of the routine study schedule.

6.4 Additional Care of Subjects

Subjects who complete the study through Visit 12 (96 weeks of follow-up) will be offered participation in a long-term safety and efficacy study as detailed in a separate protocol that will be initiated for further evaluation of the safety and efficacy durability. The long term safety study will be conducted according to current regulatory authority recommendation.

7 DESCRIPTION OF STUDY PROCEDURES

7.1 Informed Consent

Prior to entering the study, the Investigator will explain to each subject (and the subject's parent/legal guardian if the subject is under the legal age of consent) the nature of the study, its purpose, procedures, expected duration, alternative therapies available, and the benefits and risks involved in study participation.

If the subject is of the legal age of consent, they will be given the Institutional Review Board (IRB)/Independent Ethics Committee (IEC)-approved ICF to review and the opportunity to ask questions. The subject will be informed of their right to withdraw from the study at any time without prejudice. The subject should be able to answer simple questions about the study after the ICF has been reviewed and explained. After this explanation and before any study-specific procedures have been performed, the subject will voluntarily sign and date the ICF to indicate the desire to participate in the study. If the subject is unable to read the informed consent document, presence of an impartial witness is required to confirm the contents of the document were explained to the subject. The impartial witness must sign the ICF. The subject must always be asked to sign or mark the form regardless of their vision. The Investigator will also sign and date the ICF. The time (hour and minute) the consent is signed must also be recorded by the subject or legal guardian and the person providing consent to the subject. Prior to participation in the study, the subject will receive a copy of the signed and dated consent form along with an emergency card with contact information for the Investigator and clinical facility staff in the event of a medical emergency during the trial.

If the subject is under the legal age of consent, the potential subject's parent or legal guardian will be given IRB/IEC-approved ICF to review and the subject will be given an IRB/IEC-approved pediatric assent form. Both the subject and the parent/legal guardian will be given the opportunity to ask questions. Both the subject and their parent/legal guardian will be informed of the subject's right to withdraw from the study at any time without prejudice. The subject and their parent/legal guardian should be able to answer simple questions about the study after the ICF and assent form have been reviewed and explained. After this explanation and before any study-specific procedures have been performed, the parent/legal guardian will voluntarily sign and date the ICF to indicate their informed consent for the subject to participate in the study. The subject will sign and date the pediatric assent form to indicate their desire to participate in the study. The Investigator will also sign and date the ICF and assent form. The time (hour and minute) the consent and assent are signed must also be recorded by the subject (on the assent form), the parent/legal guardian (on the ICF), and the person providing consent/assent (on both forms). Prior to participation in the study, the subject's parent/legal guardian will receive copies of the signed and dated consent and assent forms along with an emergency card with contact information for the Investigator and clinical facility staff in the event of a medical emergency during the trial.

7.2 Demographics and Other Clinical Evaluations

7.2.1 Demographics, Medical History, and Prior Medications

After subjects have signed an ICF for the purpose of this study, each subject's comprehensive medical history will be recorded, including medical and demographic information (according to national data collection regulations). All prior medications including prescription and non-prescription medications and preparations and health and/or dietary supplements taken by the subject within the previous 30 days will also be recorded. In addition, hospitalizations in the past 3 months and the reason for admission (medical/surgical/psychiatric/other) in the past 3 months will also be recorded.

7.2.2 Pregnancy Testing

Blood samples for serum pregnancy testing will be collected at the Screening Visit (Visit 1) for women of childbearing potential. Testing will be conducted at the central laboratory unless it is determined that the results will not be received from the central laboratory in time for Visit 2, in which case a local laboratory may be used. The results of this test must be available and documented at Visit 2. Samples will be handled according to a standardized procedure. This procedure will be provided to the Investigator centers prior to study start. Subjects with positive pregnancy tests will be excluded from study participation.

7.2.3 Virology

Blood samples for HIV testing will be collected at the Screening Visit (Visit 1). Testing will be conducted at the central laboratory unless it is determined that the results will not be received from the central laboratory in time for Visit 2, in which case a local laboratory may be used. The results of this test must be available and documented at Visit 2. Samples will be handled according to a standardized procedure. This procedure will be provided to the Investigator centers prior to study start. Subjects with positive tests for HIV will be excluded from study participation.

7.2.4 ND4 (G11778A) Genotyping

All subjects will be required to have a blood sample taken at Visit 1 for genotyping analysis by the central study laboratory. Subjects with previously documented G11778A ND4 mitochondrial mutation can proceed to visit 2 without the results of the central laboratory genotyping. Subjects without previously documented G11778A ND4 mitochondrial mutation will be required to have the results of the central laboratory genotyping available for Visit 2. Samples will be handled according to a standardized procedure. The testing will be analyzed by the central laboratory. This procedure will be provided to the Investigator centers prior to study start. The presence of the G11778A ND4 mitochondrial DNA mutation must be documented at Visit 2 (Inclusion Visit).

7.3 Ophthalmic Evaluations

Detailed descriptions of all the ophthalmic evaluations will be detailed in the Ophthalmic Evaluations Manual. A central reading center will be used in quality control and analysis as detailed per evaluation in the Ophthalmic Evaluations Manual.

7.3.1 Visual Acuity

Enrolled subjects will include those able to read letters on the ETDRS chart ("on-chart" subjects) and those unable to read letters on the ETDRS chart but able to count fingers of the examiner at a given distance ("off-chart" subjects). On-chart subjects will have visual acuity measured with the ETDRS chart and an ETDRS score will be calculated. On-chart subjects will also have a Snellen acuity obtainable from the number of lines read on the ETDRS chart.

Off-chart subjects included in the study must maintain the visual ability to allow them to count fingers of the examiner as per the selection criteria. Off-chart subjects will not have an ETDRS score or a Snellen acuity obtainable from the ETDRS chart. Snellen acuity will be obtained utilizing the measured distance at which the subject was able to count the fingers of the examiner and a standardized formula available at (Karanjia 2014):

http://www.countfingers.com/

The Snellen acuities of on-chart and off-chart subjects will be converted to LogMAR for statistical analysis. Snellen acuities will be transformed to LogMAR using the standard formula available at:

http://www.myvisiontest.com/logmar.php

Additionally, 1 ETDRS line is considered equivalent to 0.1 LogMAR.

The visual testing at Visit 4 will be conducted for safety purposes and will not be analyzed as efficacy data (see Section 7.6.3).

7.3.2 Refraction for Best Corrected Visual Acuity

BCVA is defined as the best visual acuity that can be achieved by a subject with vision correction (e.g. glasses or contact lenses). Refraction testing for BCVA will be conducted at the Screening Visit (Visit 1) and Inclusion Visit (Visit 2) and at each follow up study visit at which visual acuity testing is conducted.

7.3.3 Spectral Domain Optical Coherence Tomography

SD-OCT will be obtained with the Spectralis® OCT (Heidelberg Engineering). Parameters will be obtained for the optic nerve (retinal nerve fiber layer) and posterior pole per standard protocols included in the Spectralis software. A central reading center will perform quality control, analysis and interpretation of all SD-OCT data.

7.3.4 Visual Field Assessment

Standardized automated visual fields will be obtained with an HVF Analyzer II (Carl Zeiss Meditec Inc.) using the 30-2 SITA Fast strategy, Stimulus III White to measure MD in decibels of sensitivity. A central reading center will perform quality control, analysis and interpretation of all HVF results.

7.3.5 Contrast Sensitivity

Assessment of the effect of IMP on contrast sensitivity will be measured with the Pelli-Robson chart.

7.3.6 Color Vision

Assessment of the effect of GS010 on color vision will be assessed using a Farnsworth-Munsell 100 Hue color vision test.

7.3.7 Color Fundus Photos

Color fundus photos will be obtained at Visit 1 to establish a baseline. Color fundus photos will be obtained at Visit 4 through Visit 12 as necessary when required for grading of vitreous inflammation.

7.5 Clinical Laboratory Tests

For any test abnormality deemed clinically significant, an AE should be recorded (unless the result was considered erroneous) and repeat analysis will be performed until resolution or until the Investigator determines that resolution of the laboratory abnormality is not expected.

[figure not shown]

7.5.5 Laboratory Results Review

It is the Investigator's responsibility to review the results of all laboratory tests as they become available. This review will be documented by the Investigator's dated signature on the laboratory report. For each abnormal laboratory test result, the Investigator needs to ascertain if this is a clinically significant abnormal change from baseline for that individual subject.

7.7 Protocol Deviations

Any protocol deviation related to the conduct of the trial, subject management, or subject assessment will be discussed with the Investigator on a case by case basis and documented. Protocol deviations will not be approved prospectively.

8 STUDY DRUG MANAGEMENT

8.1 Description of GS010

AAV is a small parvovirus that infects humans and other primate species. The vector used in this study is a recombinant form of the serotype 2 of the AAV2 vector, rAAV2/2, encoding the human *ND4* gene under the control of the cytomegalovirus immediate early promoter in an intron-containing expression cassette (beta globin intron, *HBB2*), flanked by the viral inverted terminal repeats. The construct includes the cis-acting elements of the human *COX10* mRNA (mitochondrial targeting sequence 5' of the complementary DNA [cDNA], and the 3'untranslated region at the 3' end of the cDNA) ensuring the efficient mRNA targeting to mitochondria and delivery of the corresponding protein.

8.1.1 Formulation

GS010 (rAAV2/2-*ND4*) drug product is a sterile suspension of purified viral vector formulated in balanced salt solution (BSS) plus 0.001% Pluronic F68[®]. It is filled in vials and stored frozen at \leq -70°C ready for intended medical use. Details on the preparation of GS010 IMP for administration to subjects are described in the Pharmacy Manual.

8.1.2 Storage

IMP is stored at ≤-70°C in a freezer under the supervision of the study pharmacist or the Investigator. The IMP vials will be dispensed only with the written authorization of the Investigator or his/her delegate that has been specifically designated to this study. After reconstitution (see Section 8.3), the IMP may be stored for up to 12 hours at 2 to 8°C before injection.

GS010 IMP must be kept in a locked and restricted access storage facility.

8.2 Packaging and Labeling

GS010 IMP is individually packaged. The primary label on the vial as well as secondary container labeling is in the country-specific language for each site. The labels are compliant with local regulatory requirements. The primary and secondary packaging together comply with the labeling requirements.

Packaging of IMP will be compliant with the International Air Transport Association (IATA) regulation for genetically modified organisms.

GS010 IMP will be shipped on dry ice (with 1 probe for temperature monitoring during transport).

8.3 Dose and Administration

GS010 IMP reconstitution will be performed at the site pharmacy according to the reconstitution protocol described in the Pharmacy Manual. Reconstitution kits will be

supplied by the Sponsor. The Pharmacy Guide and the Guide for Intra-Vitreal Injection of GS010 (rAAV2/2-ND4) and Sham Procedures will describe all details for preparation and proper handling of GS010 IMP.

GS010 IMP will be administered on Day 0 (Visit 3) via a single IVT injection in one eye of each subject. The dose of GS010 to be administered is 9E10 vg/eye. The injection will be performed in the vitreous humor under local anesthesia. The volume of the injected formulation is 90 μ L.

Sham IVT injection will be performed on the fellow eye (i.e. the one not randomized to receive GS010). Sham procedures will be performed by applying pressure to the eye at the location of a typical procedure using the blunt end of a syringe without needle.

IVT injection and sham procedures, including pre- and post-procedure steps, will be performed according to the Guide for Intra-Vitreal Injection of GS010 (rAAV2/2-ND4) and Sham Procedures.

8.4 Dispensing and Accountability

GS010 IMP will only be dispensed, according to Investigator's prescription, to eligible subjects who meet all selection and inclusion criteria and according to the treatment scheme.

GS010 IMP will be tracked during the handling process from prescription to destruction (through dispensation, reconstitution, administration and decontamination).

The Investigator or, depending on center organization, the Pharmacist or the person responsible for study medication management will keep an IMP accountability log detailing the dates, batch number and quantity dispensed for each subject.

Accountability records will be verified by the study monitor during site visits. All used and unused GS010 IMP vials will be recorded.

At the end of the study, all unused GS010 IMP vials will be destroyed at the investigation center following internal procedures for genetically modified organisms (GMOs). A copy of the certificate of destruction should be made available to the sponsor.

GS010 IMP accountability is ultimately the responsibility of the Investigators. This responsibility however may be delegated to the Hospital Pharmacists. This delegation will be documented in the Site Trial Master file.

8.5 Prior and Concomitant Therapy

Prior therapy is defined as prescription and non-prescription medications and preparations, including health and/or dietary supplements taken within 30 days prior to signing the informed consent, but discontinued prior to signing informed consent. Concomitant therapy is defined as prescription and non-prescription medications and preparations,

health and/or dietary supplements other than GS010 IMP that the subject receives during the course of the study (i.e. any time after the signing of informed consent). This includes any medication started prior to signing informed consent and continued after signing.

Idebenone must be completely discontinued for at least 7 days prior to Visit 2 and is prohibited throughout the study. If idebenone has not been discontinued at least 7 days prior to Visit 2 and if the study protocol timeframe between the visits is respected, Visit 2 may be delayed until the 7-day period is complete.

8.6 Method of Assigning Treatment

The right eye of each subject will be randomly allocated to receive either GS010 or sham treatment in a 1:1 allocation ratio. The fellow (left) eye will receive the treatment not allocated to the right eye. Therefore, each subject will receive GS010 in one eye and sham treatment in the fellow eye. Prior to randomization, each subject's better- and worse-seeing eye will be determined. Efron's minimization method will be used in the randomization process to balance as much as possible the two treatment groups (GS010 and sham) in the better-seeing eyes.

To enroll a subject (Visit 1), the Investigator will call an interactive response system (IRS) and provide brief details about the subject to be enrolled. Each subject will receive a subject number assigned at screening, which will serve as the subject identifier throughout the study. The subject number will be required in all communication between the Investigator (or designee) and the IRS regarding a particular subject. Subject numbers will be tracked via the IRS.

To randomize a subject (Visit 2), the masked Investigator (or designee) will call the IRS and provide brief details about the subject to be randomized. Eligible subjects will be randomized in a 1:1 ratio (right/left eye), taking into account the Efron's minimization method, using the IRS.

The IRS User Guide will describe the steps of the randomization process from the subject's screening up to before IVT injection.

An algorithm with a testing hierarchy will be employed prior to randomization to determine the better- and worse-seeing eye of each subject, as follows:

- 1. ETDRS visual acuity score for subjects able to read the ETDRS chart. The eye with the higher ETDRS score is the better-seeing eye. For subjects who cannot read the ETDRS chart ("off chart" subjects) a standard study procedure will be used to determine visual acuity based on counting fingers at a given distance. The eye with the best visual acuity based on this method is the better-seeing eye. If one eye of a subject is able to read letters on the ETDRS chart and one eye cannot, the eye able to read the ETDRS chart is the better-seeing eye.
- 2. SD-OCT parameters (to be used if there is no inter-eye difference based on Criterion 1):

- i. The initial SD-OCT parameter will be the total volume of the RGC layer of the macula. The better-seeing eye will have the greater volume and quadrant thickness, unless there is macula edema. A difference of ≥5% is considered significant to determine greater volume.
- ii. The second SD-OCT parameter (to be used if there is no inter-eye difference in criteria 2i) will be the combined volume of the RGC layer of the inner and outer nasal quadrants of the macula. The better-seeing eye will be the eye with greater volume. A difference of ≥5% is considered significant to determine greater volume.
- 3. Contrast sensitivity measured with the Pelli-Robson chart (to be used if there is no inter-eye difference in criteria 1 or 2). The eye with the best Log CS (contrast sensitivity) score is the better-seeing eye.

8.8 Procedure for Unmasking

The treated/untreated eye information (GS010-treated eye versus sham-treated eye) should not be unmasked unless knowledge of the subject's eye treatment is required for the subject's clinical care and safety. The Investigator/clinical masked team will be provided with instructions to allow them to unmask the treatment via IRS. In the unlikely event that knowledge of the eye treatment assignment is necessary in order to care for a subject, the Investigator may decide to unmask the treatment allocation for safety reasons. If the eye treatment is unmasked, the Sponsor and the assigned Clinical Research Associate (CRA) must be notified within 24 hours. Documentation of unmasking should be recorded in the subject's medical record with the reason for unmasking, the date and time of the unmasking, and the names of the personnel involved.

9 ADVERSE EVENTS

The condition of the subject will be monitored throughout the study. Overall incidence of AEs and SAEs will be evaluated for the study as a whole.

An AE is defined as any untoward medical occurrence in a subject or clinical investigation subject administered a pharmaceutical product and which does not necessarily have a causal relationship with this treatment. An AE can therefore be any unfavorable and unintended sign (including an abnormal laboratory finding), symptom, or disease temporally associated with the use of a medicinal (investigational) product, whether or not related to the medicinal (investigational) product. Any event or laboratory abnormality that leads to a medical intervention, including withdrawal of IMP or significant additional concomitant therapy, will be considered an AE. Worsening of visual acuity determined by the Investigator to be due to progression of LHON will not be considered an AE.

AEs should be volunteered by the subject, be observed from examination of the subject at a clinic visit, or be from observations of clinically significant laboratory values or special examination abnormal values. AEs will not be solicited by the use of a specific list of anticipated events.

All AEs are to be assessed and recorded in a timely manner. Each AE is to be documented with reference to severity, date of occurrence, duration, treatment, and outcome. Furthermore, each AE is to be classified as being serious or non-serious. In addition, the Investigator must assess whether the AE is drug-related or not. Changes in severity of AEs and resolution dates should be documented as separate events.

AEs will be captured from the first study-related procedure through to the completion of the protocol-defined safety follow-up as defined in Section 9.5 and Section 10.3.

Surgical procedures, planned before enrolment of the subject in the study, are not considered AEs if the condition was known before study inclusion. In this case the medical condition should be reported in the subject's medical history.

Intermittent AEs will not be reported as multiple AEs. The definition of an intermittent AE is "a recurring event with the same severity, frequency, and causality."

Clinically relevant abnormal findings observed during vital signs measurements or physical examinations will be reported as AEs.

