9.1 Reporting and Documentation of Adverse Events

9.1.1 Reporting

At each visit, any AE directly observed or mentioned by the subject will be reported by the Investigator or designee on the page "Adverse Events" of the CRF (also called the "AE page"). The unmasked team will report AEs commencing at Visits 3 and 4 and the masked team will document AEs commencing at all other visits. The unmasked team will enter

eye-related AEs identified at Visits 3 and 4 into the CRF in a masked way and will perform focused follow up at subsequent visits of ocular AEs commencing at Visit 3 and Visit 4 until AE resolution or the determination that no further clinical evolution will occur. The following items must be documented:

Nature of the event with self-explanatory and concise medical terminology (indicate a diagnosis or syndrome instead of symptoms).

Date of onset and date of resolution (i.e. actual dates when the event starts and is resolved rather than dates when the Investigator is informed).

- Severity.
- Relationship to IMP.
- Relationship to study procedure.
- Outcome.
- Seriousness.
- Action taken regarding the IMP.
- Any action taken regarding the event, whether by the Investigator, the subject (as reported by the subject), or by another physician (as reported by the subject or in the subject's medical record).

AEs requiring therapy must be treated with recognized standards of medical care to protect the health and well-being of the subject. Any treatment given will be reported on the page "Concomitant medication" of the CRF.

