9.1.1.3 Outcome

The outcome of each AE will be rated as follows:

- Recovered.
- Not recovered.
- Recovered with sequelae.
- Fatal. This outcome is to be used only for the event leading to death. The outcome of all other events at the time of the death must be reported. The outcome of ongoing ones is reported as "not recovered".
- Unknown.
- Worsening. This outcome is used when an AE worsens. The new status of the event is documented as another AE on the AE page in the CRF.

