9.2 Ocular Inflammation

Specific assessment and documentation of ocular inflammation will be required. Ocular inflammation is an expected event based on preclinical NHP studies of GS010 and Phase I evaluation of GS010 in GS-LHON-CLIN-01. Specific, standardized schemes for assessing anatomic location, severity and clinical evolution will be employed. Specific scales will be used for anterior uveitis (anterior chamber) and intermediate uveitis (vitreous).

The Standardization of Uveitis Nomenclature (SUN) Working Group provided standardized methods for (1) anatomic classification of uveitis; (2) grading scheme for anterior chamber cells; (3) grading scheme for anterior chamber flare; and (4) activity of

uveitis terminology (for clinical evolution) (Jabs 2005). Investigators will grade cases of ocular inflammation according to these scales. These scales are provided in Table 1, Table 2, Table 3, Table 4, and Table 5 below.

Table 1 Anatomic Classification of Uveitis (SUN Working Group)

Туре	Primary Site of Inflammation ^a	Includes
Anterior uveitis	Anterior chamber	Iritis
		Iridocyclitis
		Anterior cyclitis
Intermediate uveitis	Vitreous	Pars planitis
		Posterior cyclitis
		Hyalitis
Posterior uveitis	Retina or choroid	Focal, multifocal, or diffuse choroiditis
		Chorioretinitis
		Retinochoroiditis
		Retinitis
		Neuroretinitis
Panuveitis	Anterior chamber, vitreous, and retina or choroid	

SUN = Standardization of Uveitis Nomenclature

Table 2 Grading Scheme for Anterior Chamber Cells (SUN Working Group)

Grade	Cells in Fluid ^a
0	<1
0.5+	1-5
1+	6-15
2+	16-25
3+	26-50
4+	>50

SUN = Standardization of Uveitis Nomenclature

^a As determined clinically. Adapted from the International Uveitis Study group anatomic classification.

^a Field size is a 1 mm by 1 mm slit beam.

Table 3 Grading Scheme for Anterior Chamber Flare (SUN Working Group)

Grade	Description
0	None
1+	Faint
2+	Moderate (iris and lens details clear)
3+	Marked (iris and lens details hazy)
4+	Intense (fibrin or plastic aqueous)

SUN = Standardization of Uveitis Nomenclature

Table 4 Activity of Uveitis Terminology (SUN Working Group)

Term	Definition
Inactive	Grade 0 cells ^a
Worsening Activity	Two step increase in level of inflammation (e.g., anterior chamber cells, vitreous haze) or increase from Grade 3+ to Grade 4+.
Improved Activity	Two step decrease in level of inflammation (e.g., anterior chamber cells, vitreous haze) or decrease to Grade 0.

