## ETDRS/LogMAR and on-chart and off-chart:

- I. 1 ETDRS line = 5 letters
- II. 1 ETDRS line = 0.1 LogMAR
- III. 0.1 LogMAR = 5 ETDRS letters
- IV. 15 ETDRS letters = 0.3 LogMAR
- V. A less positive/more negative LogMAR is an improvement of vision
- VI. An increase in the number of ETDRS letters read is an improvement of vision

On-Chart subjects: defined as being able to read at least 3 ETDRS letters on a single line on the ETDRS chart at either 4 or 1 meters

- a. Have an obtainable Snellen equivalent obtained directly from ETDRS chart
- b. Each Snellen equivalent is assigned a LogMAR value

Off-chart Subjects: defined as a subject who cannot read at least 3 ETDRS letters on a single line of the ETDRS chart at either 4 or 1 meters and thus have no Snellen equivalent obtainable from ETDRS chart

- c. These subjects are categorized as able to either count fingers (CF), detect hand motion (HM), detect light perception (LP) or are no-light perception (NLP)
- d. For those categorized as either CF or HM a method for deriving LogMAR visual acuity is pre-specified
- e. The distance at which CF/HM vision was obtained is recorded per the standard operating procedure
- f. Study database derives the LogMAR based on this distance and the finger/hand dimensions of the examiner, per pre-specified method.

Treatment-Emergent Adverse Events (TEAE)

Treatment-emergent adverse events (TEAEs) are defined as AEs that started after study treatment administration at Visit 3 or that represent an exacerbation of a condition that is present at baseline after treatment administration. Worsening of visual acuity determined by the investigator to be due to progression of LHON will not be considered as an AE. Any AE with an unknown start date will be considered treatment-emergent if the event does not stop prior to study treatment administration. AEs with partial dates are described in [Section 5.7.2](#).

Prior and Concomitant Treatment

Prior treatments will be defined as any treatments with start date and time prior to the study treatment administration date and time.

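### Protocol sections 9, 9.1.1 and 9.1.1.3 disagree on when a new adverse event record opens, and under section 9 an improvement after injection can be flagged as treatment-emergent

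*Protocol*

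**What the plan says.** Four places govern how an AE becomes a record and how the record is classified.

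- **Protocol 9, splitting.** "Changes in severity of AEs and resolution dates should be documented as separate events". The sentence covers any change in severity, up or down, and read literally it also covers resolution.
- **Protocol 9, record content.** The same section says: "Each AE is to be documented with reference to severity, date of occurrence, duration, treatment, and outcome". Duration and outcome are therefore attributes of one event. Section 9.1.1 likewise lists "Date of onset and date of resolution" among the items to document for each event.
- **Protocol 9.1.1.3, outcome Worsening.** "This outcome is used when an AE worsens", and the new status is then entered as another AE. No parallel instruction exists for improvement or recovery.
- **SAP 5.6, treatment emergence.** "Treatment-emergent adverse events (TEAEs) are defined as AEs that started after study treatment administration at Visit 3", or as AEs that represent an exacerbation after treatment of a condition present at baseline.

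On recurrence, Protocol 9 says "Intermittent AEs will not be reported as multiple AEs" and defines an intermittent AE as "a recurring event with the same severity, frequency, and causality". Protocol 9.2 says "Ocular inflammation is an expected event based on preclinical NHP studies of GS010" and requires standardized assessment of its location, severity and clinical evolution. Table 4 in that section defines activity terms, including remission.

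**The concern.** AEs are captured from the first study-related procedure, and screening can start 28 days before injection, so some AEs will be open at dosing. Whether such an AE generates a post-dose record depends on which protocol section a site follows. Nothing in the visible text says which prevails, and seven sites are planned.

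At stake is the treatment-emergent AE table. An event that began before GS010 and improved afterwards could be listed as emerging after it. In a trial of 36 subjects a few such records visibly change the incidence of a preferred term.

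The intermittent-AE rule raises a separate, smaller question. Bouts that match on severity, frequency and causality become one AE. The visible text sets no maximum gap between bouts and does not define frequency. For an expected event whose clinical evolution must be documented, the plan should say how a return after resolution is recorded.

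**Working it through.** The plan gives no figure on this point to reproduce. The check traces the recording rules into the treatment-emergent definition, using assumed histories.

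**Inputs**
- Planned randomized subjects: 36 (Protocol 5.1).
- Screening: from 28 to 2 days before injection (Protocol 4.1; SAP 3.2).
- Unit of incidence: subjects reporting the AE at least once (Protocol 12.4.5).
- Safety analysis: only AEs occurring after IMP administration (Protocol 12.4.5).

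**History A (assumed).** A grade 2 AE begins in screening, eases to grade 1 after injection, then resolves.

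| Rule followed | Records with a post-dose start | Treatment-emergent under SAP 5.6? |
|---|---|---|
| Section 9, severity changes only | 1 | Yes, first limb |
| Section 9, read literally with resolution | 2 | Yes, first limb |
| Sections 9.1.1 and 9.1.1.3 | 0 | No |

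The post-dose record satisfies the first limb on its start date alone. The exacerbation limb does not remove it, because the two limbs are joined by *or*. The post-dose filter in Protocol 12.4.5 does not remove it either.

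Effect on incidence of that term, if the affected subjects have no genuine treatment-emergent AE under it:

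- increase = k / 36, where k is the number of affected subjects
- k = 1: 1/36 = 2.8 percentage points
- k = 2: 2/36 = 5.6 percentage points

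The documents do not allow k to be estimated.

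**History B (assumed).** One subject has three bouts of ocular inflammation.

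- Same severity, frequency and causality: 1 AE record in place of 3.
- Any of the three conditions differs: the merging rule does not apply, and the bouts are separate AEs.
- Subject-level incidence: this subject contributes 1/36 either way.

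History A can therefore alter a planned table. History B alters the record of recurrence, not the planned incidence.

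**The case against.** The strongest reply is that section 9 contains one loosely worded sentence, and the more specific sections show the intended practice: one record per event with its own resolution date, and a new record only on worsening. On that reading a pre-dose AE that eases or resolves after injection yields no treatment-emergent AE. This stands as far as resolution is concerned. A reader might infer that the plan makes every resolution a new event, but sections 9, 9.1.1 and 9.1.1.3 together do not support that as a settled rule. It does not dispose of improvements in severity: section 9 covers changes in either direction, and no visible text overrides it.

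A reader might also infer that repeat bouts of inflammation are always counted once, or that event counts and the severity breakdown are distorted. The documents do not support these readings:

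- Merging requires equal frequency and causality as well as equal severity.
- The visible incidence measure is per subject, not per event.
- Inflammation is also graded on the scales in Protocol 9.2 and summed in the Ocular Inflammation Score in SAP 5.6. Neither depends on the number of AE records.
- Protocol 12.4.5 defers AE details to the SAP, where the safety-analysis text appears to be redacted. A rule on maximum severity, or on collapsing linked records, may be there.

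The last point also limits the treatment-emergence concern. The visible definition in SAP 5.6 lacks a safeguard, but one could exist in text that cannot be seen.

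**Conclusion.** The point holds as an inconsistency with a traceable consequence. Three protocol sections differ on when a new AE record opens. If section 9 is followed, a pre-dose AE that only improves after injection meets the visible treatment-emergent definition, contrary to the evident purpose of its exacerbation limb. Each affected subject can add 2.8 percentage points to the term. This assumes 36 subjects in the safety population, no genuine treatment-emergent AE under the same term in that subject, and no redacted rule that collapses linked records.

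The intermittent-AE rule needs reconciling with section 9.2, but this is a matter of clarity. It does not change the proportion of subjects with inflammation. The point is minor overall, affects safety tabulation only, and has no bearing on the primary efficacy analysis.

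**What to change.** 1. **Protocol 9, 9.1.1 and 9.1.1.3.** Reconcile the wording so that an improvement or a resolution updates the existing AE and does not open a new one. Carry the same wording into the CRF completion guidelines.
2. **SAP 5.6.** Add a sentence: linked records of one event are treatment-emergent only if the event began after Visit 3 or its severity rose after Visit 3.
3. **Protocol 9 and 9.2.** Reconcile the intermittent-AE rule with the requirement to document the clinical evolution of ocular inflammation, and state how a recurrence after resolution is recorded. No grade-based definition of an episode is proposed here; that choice belongs to the sponsor and should agree with the terms in Table 4.

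The cost is a few sentences, a guideline update and a small programming step to link records already entered under section 9. No visit, assessment or treatment changes. If the redacted SAP safety text already handles linked records, item 2 reduces to a cross-reference.
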